#### Wilcoxon signed-rank test

```

**Read the imputed dataset for study eye;
data eff2;
  set outdata1;

```

```

chg=aval-baseline;
achg=abs(chg);
run;

**ignore zero values;
proc rank data=eff2 (where=(chg ne 0)) ties=mean out=rank;
  by _imputation_ visit treatment;
  var achg;
  ranks rchg;
run;

proc sort data=rank;
  by _imputation_ visit treatment chg;
run;
** distinguish negative and positive values;
data sign;
  set rank;
  by _imputation_ visit treatment chg;
  if chg <0 then type="Neg";
  else if chg >0 then type="Pos";
run;

proc sort data=sign;
  by _imputation_ visit treatment type rchg;
run;
** calculate sum of positive and negative ranks separately;
data sign2;
  set sign;
  by _imputation_ visit treatment type rchg;
  if first.type then cum_sum=rchg;
  else cum_sum+rchg;
  if last.type;
  keep _imputation_ visit treatment type cum_sum;
run;

**Calculate Wilcoxon location parameter;
proc transpose data=sign2 out=sign3;
  by _imputation_ visit treatment;
  var cum_sum;
  id type;
run;

** Calculate number of observations for each treatment;
data sign4;
  set sign3;
  pos1=pos;
  neg1=neg;
  if pos= . then pos1 = 0;
  if neg= . then neg1 = 0;
  pos = pos1;
  neg = neg1;
  stat=abs(neg-pos)/2;
  keep _imputation_ visit treatment stat;
  drop neg1 pos1;
run;

proc sort data=sign4;

```

```

      by _imputation_;
run;
** Calculate number of observations for each treatment;
Proc freq data=rank;
  tables visit*treatment*achg/out=counts;
  tables visit*treatment/out=freq (rename=(count=n));
  by _imputation_;
run;

data cfactor;
  set counts (where=(count>1));
  ci=count*(count-1)*(count+1);
run;
** calculate correction factor;
data cfactor2;
  set cfactor;
  by _imputation_ visit treatment;
  if first._imputation_ then cum_c=ci;
  else cum_c+c;
  if last.treatment;
run;

** Perform Wilcoxon test;
data final;
  merge freq (keep=_imputation_ visit treatment n)
  cfactor2(keep=_imputation_ visit treatment cum_c) sign4;
  by _imputation_ visit treatment;
  v=(n*(n+1)*(2*n+1)-cum_c)/24;
  tderr=sqrt((n*v-stat**2)/(n-1));
  est=stat/stderr;
  p=2*(1-probt(test,n-1));
run;

**verify location parameter calculated manually is same as the one from
SAS procedure;
ods output TestsForLocation=location(where=(test="Signed Rank"));
proc univariate data = eff2;
  var CHG;
  by _imputation_ visit treatment;
run;
proc sort data=final;
  by visit treatment;
run;

**combine all results;
ods output ParameterEstimates = outdata3;
proc mianalyze data = final;
  by visit treatment;
  modeleffects stat;
  stderr stderr;
run;

```

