### 12.1 Efficacy Assessments

#### 12.1.1 CENTRAL CORNEAL THICKNESS BY ULTRASOUND PACHYMETRY

CCT will be measured at all scheduled visits for both eyes at approximately the same time of day  $\pm$  60 minutes, always before noon (local time) and always performed before IOP measurements. Every effort should be made to ensure that the same individual performs the measurement and uses the same device for a given subject at each visit. Five consecutive measurements of CCT will be measured for each subject, for each eye at each visit. The mean CCT and SD of the five readings will be recorded, and the mean will be analyzed for efficacy.

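### SAP 12.2, MI signed-rank code: an arm and visit without tied absolute changes gets no variance, so its planned sensitivity p-value can be missing; three lesser slips barely move p

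*SAP*

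**What the plan says.** SAP 12.2 plans signed-rank p-values within each arm as a sensitivity analysis of the Week 4 change in CCT. For observed data the test comes from PROC UNIVARIATE. For the 20 imputed datasets the SAP prints its own code, offered as example code to be employed at the analysis and pooling steps. The relevant lines, under the heading Wilcoxon signed-rank test, are:

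- Tied values only are kept for the correction: "set counts (where=(count>1".
- Each tied group contributes "ci=count*(count-1)*(count+1", that is t³ − t.
- The running sum restarts only at a new imputation: "if first._imputation_ then cum_c=ci".
- The sum is merged with the counts and statistics through "cfactor2(keep=_imputation_ visit treatment cum_c) sign4".
- The variance is "v=(n*(n+1)*(2*n+1)-cum_c)/24".
- The statistic is "stat=abs(neg-pos)/2", and PROC MIANALYZE pools it through "modeleffects stat".

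On the data themselves, SAP 12.1.1 says: "The mean CCT and SD of the five readings will be recorded, and the mean will be analyzed for efficacy". The precision to which that mean is recorded is not given.

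**The concern.** The tie correction should be zero when there are no ties. Here it is missing, and SAS arithmetic on a missing value gives a missing result, so the variance and standard error disappear for that cell. The author foresaw the same problem for the rank sums, where missing `pos` and `neg` are set to 0, but has no such line for `cum_c`. The code's built-in check compares only the location statistic with PROC UNIVARIATE, so it would not reveal a missing variance.

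Three further points look wrong: the divisor on the tie term, a tie sum that is not restarted for each visit and arm, and the removal of the sign before pooling. At stake is one pre-specified sensitivity result per arm, which a programmer would otherwise have to repair after database lock.

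**Working it through.** **Inputs.** Up to 20 subjects per arm, SD 60 µm, mean change 34.6 µm (a reduction, so -34.6), two-sided alpha 0.10 (SAP 5); 20 imputations (SAP 12.2). Assumed, because the documents do not say: 2 of 20 values imputed, and recording precision of 1, 0.2 or 0.1 µm.

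**The plan's own figure.** The code states no number. The nearest one, 80% power for the one-sample t-test at effect size 0.577 and n = 20, reproduces: noncentral t with 19 df gives 0.8001.

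**1. Missing variance.** An imputation-by-visit-by-arm cell with no repeated absolute change has no row in `cfactor2`. After the merge `cum_c` is missing, hence `v` and the standard error are missing. For 20 untied values the variance should be 20·21·41/24 = 717.5.

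Observed changes, and the worst-observation replacements of Step 2, are the same in all 20 datasets. The imputed draws are continuous and unrounded, so they essentially never tie. A cell is therefore tied in all 20 datasets or in none, and every simulated run showed this.

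How often none: with 18 observed values there are 18·17/2 = 153 pairs. For a normal change with mean μ and SD σ recorded to precision d, the chance that a pair ties in absolute value is about d·[1 + exp(−μ²/σ²)]/(2σ√π) = d·(1 + 0.717)/212.7 = 0.00807·d. The chance of no tie is about exp(−153·0.00807·d).

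| Precision | Approximation | Simulation (1,500 runs) | At least one of the two Week 4 arms |
|---|---|---|---|
| 1 µm | 29% | 28% | 1 − 0.72² = 48% |
| 0.2 µm | 78% | 77% | 1 − 0.23² = 95% |
| 0.1 µm | 88% | 89% | 1 − 0.11² = 99% |

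The last column uses the simulated shares and treats the arms as independent. With all 20 values observed (190 pairs) the approximation gives 22%, 74% and 86%.

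**2. Tie divisor.** For changes {-3, -3, 5, 8, -8, -8, 10, 12}, n = 8 and the tie sum is 6 + 24 = 30. Enumerating all 2⁸ sign patterns gives an exact variance of 50.375. Divisor 48 gives 1224/24 − 30/48 = 50.375; the SAP line gives (1224 − 30)/24 = 49.75. At n = 20 one tied pair gives 717.375 correctly and 717.25 by the SAP line, a difference of 0.02%.

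**3. Carry-over.** In one emulated imputation the sum ran 6, 18, 24, 36, 60 over cells whose own terms were 6, 12, 6, 12, 24. Divisor and carry-over together lowered the variance by about 0.3% or less and p by about 0.0002 or less (Week 4 BID: 0.0755 correct, 0.0753 by the code). The one untied cell in that emulation had p = 0.0024 after correction and none from the code.

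**4. Dropped sign.** Pooling the absolute statistic changes p only when the statistic changes sign across imputations: 3-4% of runs at the assumed effect, 42-59% under no effect (the upper figure with 4 values imputed). It lowered p by up to 0.38, but the smallest altered p was 0.13 and the rejection rate at 0.10 did not change.

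**The case against.** The strongest reply is that this is example code for one secondary check. The primary analysis is on observed data with t-tests, its signed-rank check runs through PROC UNIVARIATE, and the MI t-tests and ANCOVA do not use this block. That stands and limits the point to the MI signed-rank entries of Table 14.2.1.2. It is also true that a blank p-value would probably be noticed.

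Some printed tokens (`cum_c+c`, `tderr=`, `est=`) may be letters lost when the PDF was read, so they are not counted as errors. The missing variance does not depend on them. If `cum_c+c` is literal, `c` is undefined and adds nothing, and the first tie term of an imputation is carried to every later tied cell; the carry-over remains.

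A reader might infer that the pooled result would silently rest on those imputations that happen to contain a tie. The documents do not support that: ties come from values common to all 20 datasets, so no tie-selected subset is pooled. Nor can untied cells be called the usual case. That is so at 0.2 µm or finer but not at 1 µm, and the precision is not stated.

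There is also a fair reason for the absolute value: the per-dataset p-value line needs a non-negative statistic. Signing the statistic alone would break it. For n = 20 and S = -60 without ties, the standard error is √[(20·717.5 − 3600)/19] = 23.79 and t = -2.52, so that line would return 1.979 instead of 0.021.

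**Conclusion.** The code is wrong as printed, and one of its four faults matters. For an arm and visit without tied absolute changes it yields no variance in any imputation, so the planned MI signed-rank p-value is missing. Under the stated assumptions that is about 28% of cases at 1 µm, 77-78% at 0.2 µm and 88-89% at 0.1 µm. How PROC MIANALYZE treats a missing standard error is not described in the SAP, but with all 20 missing there is nothing to combine.

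The divisor and the carry-over are errors of principle with negligible effect at n = 20. The dropped sign makes p too small only where the statistic straddles zero, and it changed no decision at 0.10 in the runs made. It would be tempting to conclude that the non-parametric support for the primary result fails, or that the sensitivity p-values are materially biased. Neither follows: the observed-data test is intact, and the real risk is a gap in one table. This is a minor correction, worth making before lock.

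**What to change.** In the MI signed-rank block of SAP 12.2:

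- After the merge, set `cum_c` to 0 when it is missing.
- Restart the tie sum at `first.treatment` and accumulate `ci`.
- Compute v = n(n+1)(2n+1)/24 − cum_c/48.
- Pool the signed statistic (pos − neg)/2.
- Use abs(test) in the per-dataset p-value line, so that p stays between 0 and 1.

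Then run the block on one tied and one untied cell and confirm the variance: 717.5 for 20 untied values, 50.375 for the eight-value example above. The cost is a few lines of example code and a short test. No data, endpoint or table changes.

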### Wilcoxon rank sum test

```

<data outdata1;
  set outdata1;
  if treatment = "Netarsudil QD" then treatment1 = "1";

```

```

else treatment1 = "2";
treatment = treatment1;
drop treatment1;
run;>
proc sort data = outdata1;
  by visit _imputation_;
run;
ods output WilcoxonScores = outdata2 (where=(class="1"));
proc npar1way data = outdata1 wilcoxon;
  by visit _imputation_;
  class treatment;
  var chg_cct;
run;

data outdata2;
  set outdata2;
  by visit _imputation_;
  mean = (sumofscores - expectedsum);
  if mean > 0 then mean1 = mean - 0.5;
  else mean1 = mean + 0.5;
  mean = mean1;
  stderr = stddevofsum;
  drop mean1;
run;
ods output ParameterEstimates = outdata3;
proc mianalyze data = outdata2;
  by visit;
  modeleffects mean;
  stderr stderr;
run;

```

Robustness analysis will also be performed on mITT population using LOCF imputation as well as using PP population ODO (see Section 8.2.1 for additional imputation details).

### 12.3 Secondary Efficacy Analyses

The secondary efficacy analyses will be conducted on the mITT population ODO. Descriptive statistics will be presented by treatment group for both study eye and qualified fellow eye. Summarization and analysis of the mean change from baseline in BCVA at Weeks 4 and 8 and mean change from baseline in mean CCT by ultrasound pachymetry at Week 8 will be completed using a similar strategy as for the primary endpoints described in Section 12.2.

Testing of the proportion of subjects who gained  $\geq 15$  letters (3 lines) in BCVA at Weeks 4 and 8 (separately) and testing of the proportion of subjects with complete resolution of corneal edema at Weeks 4 and 8 (separately), will be completed using logistic regression with fixed effects of treatment and corresponding baseline measure. The adjusted odds ratios, marginal proportion of each treatment group, and difference in marginal proportions along with corresponding two-sided 95% CIs and p-values will be presented. When none of the subjects in both treatment groups achieve a gain of 3 lines in BCVA, no inferential statistics for the testing of the proportions will be produced. Treatment comparisons will also be made using Pearson's chi-squared test or Fisher's exact test if any of the cell counts are less than five as a sensitivity analysis.

Example SAS® code for analyzing categorical outcomes ("Y" when desired criterion is met, "N" if not)

Logistic regression for modeling the treatments effect on outcome:

```
proc logistic data = indata descending alpha = 0.05;
  class treatment (ref = 'BID') / param=glm;
  model outcome = treatment baseline_BCVA;
  lsmeans treatment / diff oddsratio cl exp;
  ods output ParameterEstimates = pe;
run;
```

In the logistic model for the probability of outcome = Y, the following call to "Margins" (a SAS macro) estimates the treatment predictive margins and their difference (the margin effect) and reverses the direction of the difference (QD – BID rather than default BID – QD):

```
%Margins(data = indata,
  class = treatment,
  response = outcome,
  roptions = event='Y',
  model = treatment baseline_BCVA,
  dist = binomial,
  margins = treatment,
  options = cl diff reverse)
```

Chi-Squared test / Fisher's Exact test for comparison between treatments:

```
proc freq data=indata;
  tables outcome*treatment / chisq fisher;
  weight count/zeros;
run;
```

Robustness analysis for secondary efficacy endpoints will be performed using PP population ODO. In the summaries using PP population ODO, subjects whose dosing regimen was increased from QD to BID starting from Week 4 will be reported separately from the subjects who did not change regimens throughout the study duration under a group called "Netarsudil QD to BID" for the Week 8 visit. The baseline value for these subjects will remain the same. At Week 8 visit, comparisons for efficacy endpoints between subjects treated under QD and subjects who switched from QD to BID will be performed as appropriate. However, a high degree of caution should be exerted when interpreting the results as sample sizes might be smaller.

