## 3. Study Design and Procedures

### 3.1 General Study Design and Plan

This is an 8-week, randomized, open-label, multicenter, efficacy and safety study in subjects with FCD.

The study will be conducted at approximately 20 sites in the USA. Two different dosing regimens (QD and BID) of netarsudil will be investigated for their efficacy in reducing or resolving corneal edema in subjects with FCD. Subjects randomized to the netarsudil QD dosing regimen will be instructed to instill one drop of the Study Artificial Tear in their study eye every morning, and one drop of netarsudil in their study eye

every evening. Subjects randomized to the netarsudil BID dosing regimen will instill one drop of netarsudil in their study eye every morning and evening.

CCT will be measured by ultrasound pachymetry at approximately the same time of day  $\pm$  60 minutes and always before noon (local time), at each of the 5 scheduled visits (Screening, Baseline [Day 1], Week 2, Week 4, and Week 8/Exit). In order to be eligible to participate in the study, subjects will have been diagnosed with visually significant central corneal edema due to FCD, in at least one eye, for no longer than 12 months' duration.

At the Screening visit, the subject's diagnosis of FCD will be confirmed and CCT measured using an ultrasonic pachymeter. IOP and BCVA will also be collected.

At the Baseline visit (Day 1), the eligibility assessments conducted during Screening will be repeated to ensure that the subject meets all criteria for enrollment in the study. The same eye must qualify at both the Screening and Baseline visits. If qualified, the subject will be provided with the V-FUCHS patient reported visual disability questionnaire (Wacker 2018). The subject will be randomized (1:1) into the study and provided with study medication. The subject will also be trained on appropriate techniques for applying eye drops.

At the Week 2 and Week 4 visits, the subject will return to the study site for efficacy and safety assessments.

At the Week 4 visit, any subject randomized to netarsudil QD who, in the opinion of the Investigator, has not responded adequately to treatment, may have their netarsudil dosing frequency increased to BID for the remainder of the study. For these subjects, the morning administration of Study Artificial Tear will be terminated.

At the Week 8 visit, a final assessment of efficacy and safety parameters will be conducted, and the subject will exit the study.

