### **7.1 Modified Intent-to-Treat (mITT) Population**

The mITT population will include all randomized subjects who have received at least one dose of study medication. This population will be the primary population for efficacy analyses and will be used to summarize a subset of efficacy variables and will summarize subjects as randomized.

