#### **8.2.2 MISSING DATA HANDLING FOR EFFICACY VARIABLES**

The primary analysis will be completed with available data per subject from the mITT population.

Robustness analyses will also be presented based on the multiple imputation (MI) methodology under different assumptions of missingness and intercurrent events, using last observation carried forward (LOCF), and using the PP population with available data per subject. Imputation using MI or LOCF will

only be performed on study eye missing data at post-baseline scheduled visits. No imputation will be performed for missing fellow eye data and unscheduled post-baseline visits.

Intercurrent events will be primarily handled in the following manner:

1. Discontinuation of study medication and non-optimal compliance will be ignored, values measured after discontinuation of study medication or regardless of compliance will be used in the analyses [treatment policy strategy].
2. Withdrawal due to lack of efficacy or AEs: missing data will be singly imputed as the worst within subject observation prior to the intercurrent event [hypothetical strategy]. For efficacy variable CCT, the worst is the maximum within subject observations. In addition, the worst observation should come from post-baseline scheduled and unscheduled visits prior to the intercurrent event.
3. Missing data without withdrawal or withdrawal due to reasons other than lack of efficacy or AEs: missing data will be imputed employing MI fully conditional specification (FCS) regression method.

For the LOCF imputation, only the observations from post-baseline visits including scheduled, unscheduled, and early termination visits for a given subject will be carried forward.

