## 13. Safety Analyses

All safety analyses will be conducted using the safety population. For visit-based safety summaries (BCVA, biomicroscopy, IOP, and vital signs), subjects who switched dose group from QD to BID starting from Week 4 will be reported under treatment group BID at Week 8 visit. The baseline value for these subjects will remain the same.

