### 13.1 Adverse Events

An AE is defined as any untoward medical occurrence associated with the use of a drug in humans, whether or not the event is considered drug-related. An AE can therefore be any unfavorable and unintended sign (eg, an abnormal laboratory finding), symptom, or disease occurring after the first dose of study drug, without any judgment about causality. Any pre-existing medical condition that worsens after first administration of the study drug will also be considered a new AE. The AE reporting period starts from the time the subject signs the informed consent until the subject's last study visit. All AEs will be coded using MedDRA Version 23.0.

A treatment-emergent adverse event (TEAE) is defined as any event that occurs or worsens on or after the first dose of study medication. Adverse events recorded on the eCRF which began prior to treatment and remained unchanged or improved will not be included in the summary tables but will be included in the AE data listings. For all AE summary tables, a third group other than QD and BID dose group will be presented to capture the AEs for those subjects who switched the treatment dose from QD to BID starting from Week

4. The AE that began on or after the switch will be considered treatment emergent to the BID treatment; The AE that began before the switch and continued after the switch will be considered treatment emergent to the QD treatment only; if the AE worsened on or after the switch, the new AE (one with higher severity) would become a TEAE for the BID dose and the original AE would be treatment emergent to the QD dose.

An overall summary will be presented that includes the number of events and the number and percentage of subjects who experienced at least one TEAE, by treatment group. This summary will also include breakdowns of TEAEs further categorized as ocular (study eye and fellow eye separately with TEAEs occurred on both eyes counted towards study eye once and fellow eye once) or non-ocular, TEAEs by maximum severity, TEAEs by maximum relationship to study medication, TEAE by expectedness, serious TEAEs, TEAEs leading to study medication discontinuation, TEAEs leading to death.

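### At Week 8 the SAP groups subjects moved from QD to BID inconsistently, and its visit-based safety rule puts inadequate QD responders into the BID column

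*SAP*

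**What the plan says.** **The switch.** At the Week 4 visit a QD subject whose response the investigator finds inadequate "may have their netarsudil dosing frequency increased to BID for the remainder of the study" (SAP 3.1; likewise Protocol 3.1). BID subjects have no corresponding option, and the trial is open-label.

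**Four places where the SAP groups or tabulates these subjects at Week 8**

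- *Main efficacy tables.* SAP 12.3: "The secondary efficacy analyses will be conducted on the mITT population ODO". SAP 7.1 adds that this population "will summarize subjects as randomized". Switchers stay in QD.
- *Visit-based safety tables.* SAP 13: "subjects who switched dose group from QD to BID starting from Week 4 will be reported under treatment group BID at Week 8 visit". The rule names BCVA, biomicroscopy, IOP and vital signs, and the pre-treatment baseline is kept.
- *AE tables.* SAP 13.1: "a third group other than QD and BID dose group will be presented", to hold the switchers.
- *PP efficacy tables.* SAP 12.3 reports switchers at Week 8 in their own group, 'Netarsudil QD to BID', compares them with QD where appropriate, and advises caution. SAP 12.5 allows an optional as-treated mITT table with the same group.

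**Conditions.** PP efficacy analyses are dropped when PP and mITT coincide (SAP 7.2). The optional as-treated table is dropped in the same case (SAP 12.5).

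**Intercurrent events.** SAP 8.2.2 begins its list with "Discontinuation of study medication and non-optimal compliance will be ignored" and goes on to withdrawals and missing data. The planned change of regimen is not listed. SAP 15 does not mention the grouping.

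**The concern.** One reading can carry two labels. A switcher's Week 8 BCVA counts as QD in Tables 14.2.2.1 and 14.2.2.3 and as BID in Table 14.3.3.1. The biomicroscopy grades behind corneal edema resolution (SAP 12.1.3) count as QD in Table 14.2.4.1 and as BID in the biomicroscopy safety tables.

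The more serious part is selection. Entry to the switch group depends on poor response to QD. The safety rule takes these subjects out of QD and adds them to BID, where their change from baseline spans four weeks of QD and four of BID. Both columns shift, in opposite directions, for reasons unrelated to the regimens' effects. Protocol 3.2 seeks the regimen with the best balance of edema reduction and adverse effects, so the Week 8 safety columns will be read for that choice.

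On the efficacy side, the Week 8 QD column is not QD taken throughout, and nothing in the table says so. SAP 2.1 makes the between-group comparison primary for the proportions, so the label matters most for the 15-letter gain and edema resolution at Week 8.

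**Working it through.** **Inputs from the documents.** Up to 20 subjects per group, SD of CCT change 60 µm, two-sided alpha 0.10, effect size 0.577, 80% power (SAP 5; Protocol 9.3); 1:1 allocation (SAP 4.1).

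**Assumed, because the documents give no figure.** Share of QD subjects who switch, f = 0.10 to 0.40; share of a QD–BID gap closed by switching, r = 0.5 or 1; correlation of Week 4 with Week 8 change, 0.5 to 0.8.

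**1. The plan's own figure.** Noncentral t, 19 df, noncentrality 0.577 × √20 = 2.58, two-sided 0.10: power 80.01% against the stated 80%. The AE bounds also reproduce: 1 − 0.05^(1/20) = 13.9% and 1 − 0.05^(1/40) = 7.2%. These figures do not involve the switch.

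**2. The safety rule when the regimens do not differ.** Let both arms have mean μ, and let QD stayers have mean μ − a because poor responders have left. The whole QD arm still averages μ, so switchers average μ + a(1 − f)/f. The enlarged BID column then averages μ + a(1 − f)/(1 + f), and

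shown QD − BID = −a − a(1 − f)/(1 + f) = −2a/(1 + f).

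Comparing stayers with randomized BID gives −a; the as-randomized comparison gives 0. At f = 0.25 the safety rule therefore shows 1.6 times the stayers-only bias.

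A simulation (40,000 runs, 20 per arm, SD 60 µm, the worst f of QD by Week 4 change switching) gives the size of a on a CCT-like scale. Mean QD − BID in µm, true difference 0, ranges for correlation 0.5 to 0.8:

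| f (switchers of 20) | n in Week 8 safety columns, QD / BID | As randomized | Stayers vs BID | Safety rule |
|---|---|---|---|---|
| 0.10 (2) | 18 / 22 | about 0 | −5.5 to −8.6 | −10.0 to −15.8 |
| 0.25 (5) | 15 / 25 | about 0 | −12.3 to −19.3 | −19.6 to −30.9 |
| 0.40 (8) | 12 / 28 | about 0 | −18.6 to −29.5 | −26.6 to −42.3 |

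Check at f = 0.25, correlation 0.5: stayers average −42.2 against a QD mean of −30.0, so a = 12.2 and −1.6 × 12.2 = −19.5, against −19.6 simulated. In SD units the f = 0.25 row is −19.6/60 to −30.9/60, or about −0.33 to −0.52.

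CCT is only the scale here, since no safety table contains it. The same algebra applies to BCVA and biomicroscopy in so far as they track the switch decision. It would matter less for IOP or vital signs if these are unrelated to response. A strict worst-f cut is also the sharpest form of selection; a noisier judgment gives a smaller a.

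**3. The same groupings with a true gap of +20 µm (BID better), f = 0.25, r = 1.** As randomized, about +15; stayers vs BID, +7.8 to +0.4; safety rule, +0.6 to −11.2. The safety rule can hide or reverse the difference.

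**4. The as-randomized efficacy comparison.** With a uniform true gap D, the QD column carries (1 − f)D + f(1 − r)D, so the table shows D(1 − f·r):

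| f | r = 1 | r = 0.5 |
|---|---|---|
| 0.10 | 90% | 95% |
| 0.25 | 75% | 87.5% |
| 0.40 | 60% | 80% |

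For context, the two-sample 90% half-width at 20 per arm and SD 60 is about 32 µm with no switching at all, and the gap detectable with 80% power is about 48 µm.

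**5. Does the separated efficacy table always exist?** The protocol permits the switch, so switching is not in itself a deviation and need not remove anyone from PP. PP can then equal mITT with switchers present, and SAP 7.2 and 12.5 would together drop every efficacy table that separates them.

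**The case against.** The best defence is that efficacy as randomized and safety as treated are declared conventions (SAP 7.1, 7.3), so different columns are not in themselves an error. The safety tables are descriptive. The primary endpoint is at Week 4, before any switch takes effect; mean-change comparisons are primarily within group; and SAP 5 disclaims power for a stated effect. The SAP also separates switchers in the AE and PP tables and urges caution.

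Much of this stands. Four stronger readings are tempting, and the documents do not support them:

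- *That the Week 8 secondary endpoints cannot describe QD or the QD–BID difference.* Grouping as randomized keeps the randomized comparison of starting on QD, with an increase allowed, against BID. It was the least biased of the three groupings examined. What is missing is the statement of what is compared.
- *That the safety grouping spoils the efficacy estimates.* It does not enter them, and Week 8 CCT appears in no safety table.
- *That QD is bound to look better in the efficacy table.* This needs BID to be superior and switching to help within four weeks. Neither is known.
- *That the sponsor would conclude the regimens are equal.* With a half-width near 32 µm, a small Week 8 difference is weak evidence in any case.

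The convention does not rescue the visit-based safety rule. A subject with four weeks on each regimen and a pre-QD baseline was not simply treated with BID, and the SAP's own AE and PP rules recognize this.

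**Conclusion.** The point holds as an inconsistency with one consequential part. The visit-based safety rule in SAP 13 compares a QD column selected for response with a BID column that includes inadequate QD responders. It can show a difference where none exists: about −20 to −31 µm on a CCT-like scale at 25% switching, under the sharp-selection and correlation assumptions above. The real size depends on a switch rate that the documents do not give and on how closely each reading follows the investigator's judgment.

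The mITT Week 8 comparison is valid but unlabelled. If BID is better, it shows 1 − f·r of the gap. The safeguard of a separated efficacy table is conditional and can vanish although subjects have switched.

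Week 4 endpoints, BID within-group efficacy results and AE tables are unaffected. This should be corrected in the SAP; it does not threaten the primary analysis.

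**What to change.** 1. **SAP 13.** At Week 8, report switchers in a separate 'Netarsudil QD to BID' column, as the AE and PP tables do, and not under BID. State whether the ophthalmoscopy shift tables follow the same rule, since the Section 13 list does not name them.
2. **SAP 8.2.2 and 12.3.** Name the Week 4 regimen change as an intercurrent event, handled by treatment policy in the mITT analysis. Label the mITT Week 8 QD column 'QD, increase to BID allowed from Week 4' and print the number switched.
3. **SAP 7.2, 12.3 and 12.5.** Produce the separated Week 8 efficacy table whenever any subject switched, even if PP equals mITT. Add a note that its QD-only group is selected for response.

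An analysis that sets post-switch values to missing and imputes them is optional. The imputation code in SAP 12.2 covers CCT only, so BCVA would need new code. It would also have to assume that the recorded data up to Week 4 explain an investigator's judgment.

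**Cost.** SAP wording and table shells only; trial conduct does not change. The switcher column will be small (2 to 8 subjects over the range above), and the QD safety column at Week 8 stays at 18 to 12, as under the current rule.
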